A population-representative longitudinal study design (**Cohort 1 or Main cohort**) was used enrolling children aged 6 to 6.9 months from May 2021 until November 2021. In addition, a second cohort (**cohort 2 or Treatment cohort**) was constituted consisting of all children admitted to MAM OTP (French: URENAM) and SAM OTP (French: URENAS) provided by first-line health centers and community health workers from May 2021 until February 2022. Finally, study field workers home visited a subsample of children three months after their discharge from SAM or MAM OTP to assess the impact of the intervention on post-treatment relapse rates (**cohort 3 or Relapse prevention study**). While the Main cohort study is an experimental study³, the Treatment cohort and Relapse prevention study are quasi-experimental in nature. The quasi-experimental character of these two sub-studies implies that the random character of the intervention and comparison group is not fully guaranteed. More precisely, children enrolled in the Treatment cohort may not be comparable between study groups because the BCC and SQ-LNS may prevent a proportion of the usual prevalence of wasting. Similarly, a higher screening coverage or screening by family MUAC may refer children with wasting with different characteristics as compared to those in the comparison group. Therefore, any impact or lack of impact of the NASG intervention to support the OTP services needs to be interpreted with caution, as it may be a result of both the intervention and any different characteristics of the enrolled samples of children. For the same reasons, the results of the relapse prevention study must be interpreted bearing in mind possible impacts of the preceding preventive BCC and SQ-LNS and improved screening and referral (studied in the main cohort), as well as possible impacts on the adherence and recovery rates of MAM and SAM OTP (studied in the treatment cohort).

Study outcomes

Primary study outcomes

1. The longitudinal prevalence of wasting in children enrolled at the age of 6 months followed monthly until the age of 12 months or until the end of the study, whatever comes first (**cohort 1 or Main cohort**). This indicator is defined for each child as the number of visits during which nutritional wasting is observed divided by the total number of monthly visits made (by the interviewers).

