For each stratum, the president of FELASCOM drew a piece of paper (containing the name of a health center catchment area) from the bag and drew also one of the envelopes (containing the unique two-letter code). As he unfolded the piece of paper, he read aloud the name of the health center catchment area and showed the name of written on the piece of paper to all participants and wrote that name on the front of the envelope. This process continued until all 46 envelopes were linked to a health center catchment area. After this step, the IFPRI principal investigator projected the two-letter codes with study arm assignment to all participants. During this last step, the envelopes were opened one by one and the president of the FELASCOM read the name of the health center catchment area and the two-letter code aloud so that the result could be written by the secretary on a flip chart and made visible to all participants.

Sample Size

Sample sizes were calculated prior to randomization and data collection. However, as mentioned earlier, 3 study clusters were omitted from the study during the baseline survey because of severe security threats. In addition, the sponsor allowed the study to be extended by two months to the end of February 2022. We therefore recalculated the sample size for each of the primary outcomes for 42 study clusters instead of the original 45 and including two additional months of recruitment of study subjects.

Cohort 1 - Main Outcome: Longitudinal prevalence of wasting

Scenario with 45 clusters available (SAP version 1.0)

Considering a baseline longitudinal prevalence of 13.2% (obtained from the control group of the PROMIS Mali study) with a standard deviation (SD) of 0.239 for the control group and an SD of 0.189 for the treatment group, a mean cluster size of 35 (anticipating a loss of follow-up of 15%), a statistical power of 80%, a type I error of 5% and an intra-cluster coefficient of 0.04, we need at least 44 clusters to detect a minimum difference of ~ 4.84 percentage points in the 6-14 months age group.

Scenario with 42 clusters available (SAP version 2.0)

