Considering a baseline longitudinal prevalence of 13.2% (obtained from the control group of the PROMIS Mali study) with a standard deviation (SD) of 0.239 for the control group and an SD of 0.189 for the treatment group, a mean cluster size of 55 (anticipating a loss of follow-up of 15%), a statistical power of 80%, a type I error of 5% and an intra-cluster coefficient of 0.04, we need at least 42 clusters to detect a minimum difference of ~ 4.55 percentage points, , which is equivalent to a relative risk of 0.65.

Cohort 2 - Primary Outcome: recovery Rate

The aim is to include all URENAS and URENAM treatment data for children between 6 and 23 months of age. Using 2019 health district statistics, the total number of SAM and MAM cases (6-23 months of age) over 8 months of follow-up was estimated at 750 and 1,000 respectively.

Scenario with 45 clusters available (SAP version 1.0)

With 44 clusters that each have an average of 35 cases of SAM and MAM over a 7-month period, assuming a URENAS/URENAM cure rate of 79%, a statistical power of 80%, a type I error of 5% and an intra-cluster coefficient of 0.05, a minimum difference of ~9.0 percentage points in the URENAS/URENAM cure rate could be detected in children aged 6-23 months.

Scenario with 42 clusters available (SAP version 2.0)

With 42 clusters that each have an average of 50 cases of SAM and MAM over a 7-month period, assuming a URENAS/URENAM cure rate of 79%, a statistical power of 80%, a type I error of 5% and an intra-cluster coefficient of 0.05, a minimum difference of ~9.0 percentage points in the URENAS/URENAM cure rate could be detected in children aged 6-23 months.

Cohort 3 - Primary Outcome: Prevalence of Relapse

Scenario with 45 clusters available (SAP version 1.0)

We considered a 35% prevalence of relapse in children aged 9-17 months, three months after treatment completion (estimate obtained in the control group of the PROMIS Mali study). We need a minimum of 44 clusters with a mean cluster size of 20 (anticipating a 15% loss of follow-up), a statistical power of 80%, a type I error of 5% and an intra-cluster coefficient of 0.04 to detect a minimum difference of ~ 12.0 percentage points in the 9-18⁵ months age group.

Scenario with 42 clusters available (SAP version 2.0)

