We considered a 35% prevalence of relapse in children aged 9-17 months, three months after treatment completion (estimate obtained in the control group of the PROMIS Mali study). We need a minimum of 42 clusters with a mean cluster size of 20 (anticipating a 15% loss of follow-up), a statistical power of 80%, a type I error of 5% and an intra-cluster coefficient of 0.04 to detect a minimum difference of ~ 13.5 percentage points in the 9-18 months age group.

Sampling and study inclusion criteria

Cohort 1

In May 2021 a census will be organized to enlist all households with at least one child aged 0-6 months in 3-6 villages per health center catchment area. These villages will be selected proportion to their population size. Between May and November 2021, a random sample of children meeting the study's inclusion criteria will be enrolled using these census lists.

The criteria for inclusion of children in Cohort 1 are:

- 6-6.9 months of age;
- Singleton child
- The mother does not intend to leave the study area before March 2022;
- The child does not have congenital malformations that make anthropometric measurements impossible.

Cohort 2

Anthropometry and participation data for the MAM and SAM OTP of all malnourished children between 6 and 23 months of age will be collected from the MAM and SAM OTP anonymously (i.e. personally identifiable information such as name, address and date of birth will not be collected) for mothers-children from villages not selected for cohort 1. For mothers-children from villages selected for cohort 1, informed consent to participate in the study of cohort 2 and potentially cohort 3 (if randomly selected for cohort 3) will be obtained before recording the personally identifiable information.

Cohort 3

⁵ This age range corresponds to children discharged from URENAM/URENAS treatment between 6 and 15 months (the follow-up measure for cohort 3 will be done 3 months after discharge).

A random sample of children aged 6-15 months will be selected from the lists of children declared recovered from wasting from URENAM and URENAS treatment between May and December 2021. These children will be home visited by a fieldworker 3 months after being declared cured and discharged from treatment to diagnose a possible relapse.

The criteria for inclusion of children in Cohort 3 are:

- Child ex-MAM or ex-SAM at least 3 months after being declared recovered from wasting through URENAM/URENAS treatment
- Singleton child

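### Cohort 3: losing two clusters with every other input unchanged cannot raise the detectable difference from 12.0 to 13.5 points; also, cohort 2's 50 cases per cluster does not fit its stated 7 months

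*SAP*

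**What the plan says.** The Sample Size section gives each primary outcome twice, once for the version 1.0 design and once for version 2.0. It says the recalculation covers the lost clusters and is made "including two additional months of recruitment of study subjects".

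**Cohort 3 (relapse at three months).**
- Version 1.0: "We need a minimum of 44 clusters with a mean cluster size of 20 (anticipating a 15% loss of follow-up"), "to detect a minimum difference of ~ 12.0 percentage points".
- Version 2.0: "We need a minimum of 42 clusters with a mean cluster size of 20 (anticipating a 15% loss of follow-up"), "to detect a minimum difference of ~ 13.5 percentage points in the 9-18 months age group".
- Both assume 35% relapse, ICC 0.04, 80% power and 5% type I error. The SAP states no direction of effect and does not say whether 20 is before or after the 15% loss.

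**Cohort 2 (recovery).**
- The 2019 caseload of SAM and MAM cases "over 8 months of follow-up was estimated at 750 and 1,000 respectively", that is 1,750 in total.
- Version 1.0 uses 35 cases per cluster over 7 months with 44 clusters. Version 2.0 reads: "With 42 clusters that each have an average of 50 cases of SAM and MAM over a 7-month period". Both report about 9.0 points from a 79% cure rate at ICC 0.05.
- Study design describes cohort 2 as all admissions "provided by first-line health centers and community health workers from May 2021 until February 2022", which is 10 months. Statistical analysis, Data sources, assigns May–July 2021 to baseline and only August 2021–February 2022 to impact.

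**The concern.** With everything else fixed, the detectable difference varies roughly with the inverse square root of the number of clusters. Losing 2 of 44 clusters should cost about 2%, but the SAP's figure rises by 12.5% (13.5/12.0 = 1.125). Either 13.5 is wrong, or an input changed and was not disclosed. Relapse is one of three primary outcomes, and a reader cannot tell whether the result is a slip or the cohort 3 sample shrank.

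In cohort 2 the cluster size rose from 35 to 50 while the period stayed at 7 months. The reader cannot tell whether 50 includes admissions from May–July, before the programme started, which do not enter the impact analysis.

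**Working it through.** **Method.** Two-proportion comparison, two-sided 5%, 80% power, 1:1 allocation, k clusters per arm of size m. The design effect is 1 + (m − 1) × ICC, so the effective n per arm is k·m / [1 + (m − 1) × ICC]. The detectable difference d solves

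n = [z₀.₉₇₅ √(2p̄(1 − p̄)) + z₀.₈₀ √(p₁(1 − p₁) + p₂(1 − p₂))]² / d².

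Variants: unpooled or control-rate variance; t with 2k − 2 degrees of freedom in place of z; Fleiss continuity correction; m = 20 or 17 (20 less 15%); relapse falling or rising from 35%. That makes 48 combinations.

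**Check on cohort 1.** d = (t₀.₉₇₅ + t₀.₈₀) × √[(0.239² + 0.189²) × (1 + (m − 1) × 0.04) / (k·m)].
- 22 × 35: 2.868 × 0.01687 = 4.84 points (stated 4.84).
- 21 × 55: 2.872 × 0.01594 = 4.58 points, or 4.47 with z (stated 4.55).

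The general approach therefore matches the SAP's own.

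**Cohort 3, effective sample size.** At m = 20 the design effect is 1 + 19 × 0.04 = 1.76.
- 44 clusters: 22 × 20 / 1.76 = 250.0 per arm.
- 42 clusters: 21 × 20 / 1.76 = 238.6 per arm.
- √(250.0 / 238.6) = √(44/42) = 1.024.

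**Cohort 3, detectable difference (points).**

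| Convention | 44 clusters | 42 clusters |
|---|---|---|
| Fall, m = 20, pooled, z | 11.38 | 11.63 |
| Fall, m = 20, pooled, t | 11.63 | 11.90 |
| Fall, m = 20, pooled, t, continuity correction | 12.01 | 12.30 |
| Fall, m = 17, pooled, t | 12.15 | 12.43 |
| Fall, m = 17, control-rate variance, t, continuity correction | 13.25 | 13.59 |
| Rise, m = 17, pooled, t | 13.20 | 13.54 |

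- For a fall with pooled or unpooled variance, 42 clusters give 11.6–12.3 at m = 20 and 12.1–12.9 at m = 17.
- The stated 12.0 at 44 clusters is reproducible (third row).
- Some conventions reach about 13.5 at 42 clusters (last two rows), but they give 13.2–13.3 at 44, not 12.0.
- Over all 48 combinations the step from 44 to 42 adds 0.25–0.35 points (ratio 1.022–1.026), so 12.0 becomes 12.26–12.31.
- Rounding does not explain the gap: even 12.49 × 1.026 = 12.8.

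**Power at 13.5 points, 42 clusters of 20, fall to 21.5%.** With pooled variance and z: (0.135 − 1.960 × 0.04122) / 0.04075 = 1.33, giving 90.8%. Across pooled and unpooled variance, z or t, with or without correction: 87.5–91.2% at m = 20 and 84.1–88.6% at m = 17. On the same conventions, 80% power for 13.5 points needs about 30–35 clusters of 20, or 33–38 of 17.

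**What would produce 13.5.** For a fall with pooled variance and no correction, 42 clusters reach 13.5 at about 12–13 children per cluster (42 × 12 = 504 to 42 × 13 = 546, against 42 × 20 = 840), or at an ICC of about 0.07.

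**Cohort 2.**
- 750 + 1,000 = 1,750 in 8 months, so 1,750 / 8 × 7 = 1,531 in 7 months.
- 1,531 / 44 = 34.8, which matches version 1.0's 35. 1,531 / 42 = 36.5, against the stated 50.
- 42 × 50 = 2,100 cases needs 2,100 / (1,750 / 8) = 9.6 months. Ten months gives 1,750 / 8 × 10 / 42 = 52.1 per cluster.
- Detectable rise from 79%, over the same variance, z or t and correction choices: 8.4–9.0 points at 50 per cluster and 8.8–9.4 at 36.5.

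**The case against.** The best defence is that both cohort 3 figures can come from one formula if the direction of effect changed between versions. At 17 per cluster with t, a fall from 35% with 44 clusters gives 12.1, and a rise from 35% with 42 clusters gives 13.5. That may be what happened, and it needs no new cluster size or ICC. But the SAP states no such change, and solving for a rise would not suit an intervention meant to reduce relapse. It would be one more undisclosed change of input, so the two figures as printed still do not agree.

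Three further points have weight.
- The exact replacement depends on whether 20 is before or after loss: with t and pooled variance, 42 clusters give 11.9 at 20 and 12.4 at 17. The 12.3 comes from scaling the SAP's own 12.0 and is also obtained directly at 20 with t and continuity correction.
- The number of clusters was fixed by security losses, so calling 42 a minimum is loose wording and the 30–35 figure has no design consequence.
- Version 2.0 is dated September 2022, after follow-up ended in February 2022. The figure can no longer affect recruitment, and no model or decision rule uses it.

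On cohort 2, August–February is exactly 7 months, so the period may be intended and the caseload may have exceeded the 2019 figure. That is possible, but the SAP gives no such caseload.

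**Conclusion.** The point holds. On the printed inputs, and with the direction of effect kept the same, the version 2.0 detectable difference for relapse should be about 12.3 points, not 13.5. This does not depend on the choice of formula, because it rests on the ratio between two scenarios that differ only in the number of clusters. If the printed inputs are right, the error is conservative: for a fall in relapse, power at 13.5 points is about 84–91%, not 80%. If 13.5 is right, an unstated input changed, and the documents do not show which.

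The cohort 2 inconsistency is minor. At the 2019 caseload, 50 per cluster fits about 10 months of admissions and not 7, but the stated 9.0 points holds approximately at either size, taking the effect as an increase from 79%.

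**What to change.** **Cohort 3.** Restate the version 2.0 detectable difference as about 12.3 points (35% to about 23%) for 42 clusters of 20. State the direction of effect and whether 20 is before or after the 15% loss. If 13.5 is the intended figure, state the input that changed, such as smaller or unequal clusters, a larger ICC or a different direction.

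**Cohort 2.** Choose one of two statements. Either base the calculation on the August–February impact window (about 36 per cluster, about 9.0 points for an increase), or say that 50 counts all admissions from May to February and also give the difference for the impact window. If a caseload above the 2019 figure was assumed, give it.

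**Cost.** SAP wording only; no added children and no change to the analysis.

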2. The recovery rate in children enrolled at the age of 6-23 months for a treatment of up to 3 months in URENAM and URENAS treatment services and followed until their discharge (**cohort 2 or**

³ The main cohort study is an experimental cluster-randomized controlled study that guarantees (if random allocation of clusters is successful) that the samples of children enrolled in the intervention and comparison group have similar household, caregiver, and child characteristics. Therefore, any observed impacts can be exclusively associated with the intervention.

Treatment cohort). This indicator is defined as the number of children declared recovered from wasting according to the criteria of the national program (WLZ-score \geq -1.5 or MUAC \geq 125mm, and absence of bilateral edema during two consecutive visits, within 12 weeks after enrollment in the program) divided by the total number of enrolled children.

3. The prevalence of relapse after URENAS or URENAM treatment defined as the proportion of children (9-18 months of age) with WLZ-score <-2 or MUAC <125 mm or bilateral pitting edema three months after discharge from SAM or MAM OTP (**cohort 3 or Relapse Prevention study**).

Secondary study outcomes

For Cohort 1

- The longitudinal prevalence of:
 - o MAM defined as the number of MAM diagnoses divided by the total number of monthly visits made by the survey teams.
 - o SAM defined by the number of SAM diagnoses divided by the total number of monthly visits made.
- The incidence of:
 - o Wasting defined as the number of new cases of wasting diagnosed during the monthly visits made by the survey teams.
 - o MAM defined as the number of new MAM cases diagnosed during the monthly visits made by the survey teams.
 - o SAM defined as the number of new SAM cases diagnosed during the monthly visits made by the survey teams.
- The prevalence of anemia and severe anemia defined as the proportion of children with a hemoglobin level below 11g/dL and 7 g/dL respectively, at age of 12 months or at the end of the study.
- The mean hemoglobin concentration at age of 12 months or until or at the end of the study.
- The prevalence of stunting defined as the proportion of children with LAZ <-2 (according to the 2006 WHO reference) at age of 12 months or at the end of the study.

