Date of birth to calculate the child's age at study enrolment will be obtained from, in order of priority: birth certificate, vaccination card or by using a local events calendar. Child anthropometry is taken at enrolment and at each monthly visit of the longitudinal follow-up in the Main cohort and three months after discharge from SAM and MAM OTP for the Relapse prevention study. The child's weight is taken using an electronic scale (SECA 876, Germany) to the nearest 100g. The length is measured to the nearest 1 mm using length boards. The Mid-Upper Arm Circumference (MUAC) was measured using a non-stretch tape with 0.1 cm accuracy (SECA 201, Germany). All measurements are taken in duplicate by a trained anthropometrist and the study enumerator as assistant. All measurements are standardized prior to the study. Standardization exercises using repeated measurements on 10 children aged 6-23 months will be repeated every two months during the study. The MUAC, weight and height of the mother are also measured using the same equipment. The child weight-for-height and height-for-age z-scores will be calculated using the *zscore06* command in Stata⁷, which uses the World Health Organization's growth standard⁸. A wasting episode is defined as follows: it starts when a child is found to be wasted at the monthly measurement by study teams and ends when a child does not suffer from wasting at one monthly measurement. MAM and SAM episodes are defined the same way.

Child hemoglobin concentration is measured at enrolment and end of study follow-up in Main cohort, as well as in children enrolled in the Relapse prevention study. For this purpose, finger blood is collected. The hemoglobin concentration in the second drop of finger blood is measured by spectrophotometry using a HemoCue device 301 (HemoCue Ltd, Dronfield, UK). Anemia in children and severe anemia are defined by a hemoglobin concentration of less than 11 g.dl⁻¹ and less than 7 g.dl⁻¹ respectively.

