Children are enrolled in the study cohort at the age of 6 months, when the program foresees MUAC screening measurements and SQ-LNS distribution by NASG to start. From August 1th, 2021 (start of the program) onwards, NASG in both intervention and comparison study arms are tasked to conduct home visits to pregnant and lactating women and caregivers of children up to 24 months of age to provide BCC on child nutrition, health and WASH. Therefore, it is likely that caregivers with children of 6 months enrolled in the cohort after the start of the program have been exposed to BCC prior to study inclusion. This exposure to BCC may have been greater in the intervention group because in that study group the program formed new NASGs proportionate to village population size (contrary to the comparison group with typically counts 1-2 NASG per village independent of population size). For this reason, all analyses related to study outcomes on the impact pathway related to BCC (knowledge indicators, IYCF, immunization rates, WASH practices, child anthropometry) include the data at enrollment at the age of 6 months. For study outcomes related to activities that only start between the age of 6 and 7 months, like MUAC-based screening and the distribution of SQ-LNS, we consider data related to the program’s impact from the child age of 7 months onwards. To assess the intervention’s impact between study enrollment (child age of 6 months) until the end of the study (9 to 12 months of age)

Treatment of missing data for primary study outcomes

We conducted multiple imputation of missing longitudinal anthropometric data using fully conditional specification, also known as multiple imputation by chained equations which imputes missing values

under the missing at random assumption¹¹. Imputation variables were the wide-form anthropometric measurements and child age, and complete predictors (independent variables) were child sex and randomization stratum. We used 50 imputations with 10 burn-in iterations to allow for convergence to a stationary distribution before the imputation. Imputation quality will be assessed using trace plots by iteration to assess convergence and using box plots to compare distributions of observed and imputed values.

Statistical analysis methods

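### Taken literally, the SAP's episode rule counts improvement from SAM to MAM as a new MAM case and does not keep pre-existing wasting out of the three incidence outcomes

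*SAP*

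**What the plan says.** Under Secondary study outcomes, For Cohort 1, three incidence outcomes are listed:

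- "Wasting defined as the number of new cases of wasting diagnosed during the monthly visits made by the survey teams"
- "MAM defined as the number of new MAM cases diagnosed during the monthly visits made by the survey teams"
- "SAM defined as the number of new SAM cases diagnosed during the monthly visits made by the survey teams"

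None of these entries defines *new*. The one operational rule is in Measurements and indicator compilation. Of a wasting episode it says "it starts when a child is found to be wasted at the monthly measurement by study teams" and that it "ends when a child does not suffer from wasting at one monthly measurement". It then adds: "MAM and SAM episodes are defined the same way".

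Four other places bear on how this works:

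- Sampling and study inclusion criteria sets no nutritional condition for entry to cohort 1, so wasted children can be enrolled.
- Cohort 1 specific considerations keeps the enrolment visit for outcomes on the BCC pathway, a list that closes with "child anthropometry) include the data at enrollment at the age of 6 months".
- Data sources assigns May to July 2021 to baseline and August 2021 to February 2022 to the assessment of impact.
- Statistical analysis methods sends the incidence outcomes to a mixed-effects Poisson model and states no at-risk condition.

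**The concern.** An incidence outcome should count onsets among children who were free of the condition. The episode rule asks only whether the child is in the state at a visit and was not already in an open episode of that state. Two problems follow.

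**Moves between grades.** The rule is applied to MAM and SAM separately. A child seen with SAM and then with MAM closes a SAM episode and opens a MAM one, although the change is an improvement. MAM incidence then contains recoveries as well as onsets. Such moves are to be expected, because Auxiliary results has the study teams refer every MAM or SAM case they find for treatment. Wasting incidence is not touched, since the move stays within one wasting episode.

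**Disease present at the start.** No preceding visit free of the condition is required. A child wasted at the first visit opens an episode there. If enrolment is not regarded as a monthly measurement, a child still wasted at the first monthly visit opens one at that visit. For children enrolled before August, the SAP also does not say whether wasting seen at the last July visit and again in August is new. All three incidence outcomes are exposed. Cases that the intervention had no chance to prevent pull the ratio towards 1.

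**Working it through.** The SAP gives no incidence figure, expected count or power for these outcomes, so there is nothing to reproduce. Step 1 applies the rule to example children; step 2 illustrates the size.

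**Step 1. The rule applied to visit sequences**

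N = no wasting, M = MAM, S = SAM; the first position is enrolment. Counts are wasting / MAM / SAM. MAM is taken to exclude SAM. The SAP does not say so outright, but it lists wasting, MAM and SAM as three outcomes, and a MAM that included SAM would be the same as wasting.

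| Sequence | Rule as written | Preceding measurement must be free of the condition (for MAM: of MAM and SAM) |
|---|---|---|
| M-M-M-N-N-N-N | 1 / 1 / 0 | 0 / 0 / 0 |
| S-S-M-M-N-N-N | 1 / 1 / 1 | 0 / 0 / 0 |
| N-S-M-N | 1 / 1 / 1 | 1 / 0 / 1 |
| N-M-S-M-N | 1 / 2 / 1 | 1 / 1 / 1 |

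The counts in the middle column do not change if the enrolment measurement is left out. A child wasted at enrolment but recovered by the first monthly visit would then not be counted.

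**Step 2. Share of counted wasting cases already present at enrolment (illustration)**

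Inputs from the SAP:

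- p = 0.132, the control longitudinal prevalence in Sample Size, used here as prevalence at enrolment.
- D = 5.1 months, the mean length of a recovered MAM episode in the single-coverage formula, used here for all wasting.
- RR = 0.65, the planning relative risk in Sample Size, used here as a true incidence ratio.

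Assumptions: steady state, equal enrolment in each month from May to November, and the same enrolment prevalence in both arms.

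- Onsets per child-month: p / D = 0.132 / 5.1 = 0.0259.
- Monthly visits falling in August to February, by enrolment month May to November: 4, 5, 6, 6, 5, 4, 3. The mean is 33 / 7 = 4.71.
- Onsets per child in the window: 4.71 × 0.0259 = 0.122.
- Pre-existing cases per child: wasting found at enrolment in May to July opens its episode before the window, so 4 of the 7 enrolment months contribute: 0.132 × 4/7 = 0.075.
- Share pre-existing: 0.075 / (0.075 + 0.122) = 38%.
- Apparent ratio: 0.38 + 0.62 × 0.65 = 0.78.

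**Step 3. How far this moves**

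- p cancels, so the share in step 2 depends on D and the visit pattern: (4/7)D / [(4/7)D + 4.71]. D = 1.5 gives 0.857 / 5.571 = 15%, and D = 5.7 (the SAP's SAM figure) gives 3.257 / 7.971 = 41%. The apparent ratios are 0.15 + 0.85 × 0.65 = 0.70 and 0.41 + 0.59 × 0.65 = 0.79.
- For a single child followed T months, with enrolment cases counted and no calendar window, the share is D / (D + T). Over D = 1.5 to 5.7 and T = 3 to 6 it runs from 1.5 / 7.5 = 20% to 5.7 / 8.7 = 66%.
- If such a child is counted only when still wasted at the first monthly visit, D in both places becomes D × exp(−1/D), and the share runs from 11% to 62%. Over both variants the apparent ratio is 0.69 to 0.88.
- Without steady state, the share over 6 months is p0 / [p0 + 6i(1 − p0)]. Enrolment prevalence p0 of 5% to 13.2% and an assumed monthly incidence i of 2% to 5% give 15% to 56%.

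The values D = 1.5 and i = 2% to 5% are assumptions, not SAP figures. No size can be put on the SAM-to-MAM part, because the SAP gives no SAM frequency or step-down rate.

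**The case against.** **The SAP does not say that prevalent cases are counted.** A reader might infer that it does. The outcome list speaks of new cases, the episode rule does not mention incidence, and the measurement section distinguishes enrolment from the monthly visits. *New* may well be meant to exclude prevalent cases. This stands as a limit on the claim: what is shown is that the only rule given does not exclude them, so two analysts could count differently.

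**Half of all cases pre-existing.** A reader might arrive at about 50% and an apparent ratio of about 0.82 by counting an enrolment case for every child over the whole follow-up. That ignores the August to February window in Data sources. With the window, the same assumptions give 38% and 0.78. The inputs are also borrowed: an average over follow-up serves as point prevalence at 6 months, and a recovered-MAM duration serves for all wasting.

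**Enrolment wasting may be partly preventable.** Cohort 1 specific considerations keeps enrolment anthropometry on purpose, because caregivers enrolled after 1 August may already have received BCC, perhaps more in the intervention arm. This also stands. The dilution applies only to the part of enrolment wasting that the intervention does not affect, and a fix should not lose that information. It does not make a case found at enrolment an incident one.

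**A SAM benefit showing as MAM harm.** A reader might infer this from the step-down counting. Better recovery from SAM would add step-downs, but fewer SAM onsets would remove them, and study-team referral in both arms blunts any contrast. The SAP does not settle the sign.

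**Conclusion.** The point holds as a defect in the definition of three secondary outcomes. The stated rule, followed literally and with MAM excluding SAM, counts improvement from SAM to MAM as a MAM onset and can count two MAM episodes within one wasting episode. MAM incidence is therefore not a clean measure of onset, with an undetermined direction of error between arms. The same rule allows wasting already present at enrolment, or at the last visit before August, to count as new in all three outcomes.

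The figures of 38% and 0.78 illustrate size under the stated assumptions and are not estimates for this trial. Even the low end of the range, 11%, is not negligible. The primary outcome, and the longitudinal prevalence of MAM and SAM, do not use the episode rule and are unaffected.

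**What to change.** In Secondary study outcomes, For Cohort 1 and in Measurements and indicator compilation, define:

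- **Incident wasting:** wasting at a visit whose preceding measurement showed no wasting.
- **Incident MAM:** MAM at a visit whose preceding measurement showed neither MAM nor SAM.
- **Incident SAM:** SAM at a visit whose preceding measurement showed no SAM.
- **First visit:** enrolment, or the last visit before August for children enrolled earlier, sets status only and contributes no case.
- **SAM to MAM:** reported as improvement, not as a case.

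State also what is done when the preceding visit is missing. Report wasting prevalence at enrolment by arm as a separate result, so that any BCC effect before 6 months of age remains visible.

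The monthly measurements needed are already collected, so the change is one of SAP wording and programming. The price is fewer counted events, and hence less precision for these three outcomes.
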